#### **4.9.3 Time to Response:**

Time to response (TTR) for the subset of patients who achieve a CR or PR will be summarized using descriptive statistics.

#### **4.9.4 Progression-free Survival**

Progression-free survival is defined as the interval between the date of first dose and the date of disease progression (based on radiographic or clinical progression at EOT/EOS) or death, whichever occurs first. Patients who have the event after the start of subsequent anticancer therapy/procedure, or who are progression-free and alive at the time of clinical cutoff, or have unknown status, will be censored at the time of their last valid disease assessment on or before the start of subsequent anticancer therapy/procedure or clinical cut-off. When a subsequent anticancer therapy was used and progressive disease (based on radiographic or clinical progression at EOT/EOS) were observed within 6 days, they will be considered as the same visit (within the +/-6 days window) and the patient will be counted as having an event.

Patients with no post-baseline disease assessment will be censored on Day 1.

PFS will be estimated and displayed by dose levels for the efficacy analysis set using Kaplan-Meier methods (SAS® PROC LIFETEST). Patients who do not have a PFS event during or after the study will be censored. A Kaplan-Meier plot will be presented.

#### **4.9.5 Overall Survival**

Overall survival is defined as the interval between the date of first dose and the date of death from any cause. Patients who are known to be alive as of their last known status will be censored at their date of last contact. Patients who are lost to follow-up will be censored at the date the patient is last known to have been alive. The last confirmed alive date is the latest of the following: study visit date, telephone contact date, end of study last confirmed alive date, follow-up systemic (anticancer) therapy end date or start date (if ongoing or end date is missing), local or central radiologist scan date, or other date in the clinical database.

OS will be estimated and displayed by dose levels for the efficacy analysis set using Kaplan-Meier methods (SAS® PROC LIFETEST). A Kaplan-Meier plot will be presented.

The results of all peripheral white blood cell populations, DNA cross-link formation, and renal functional tests will be listed by patient.

[Redacted content]

**5 Interim Analyses**

No formal interim analysis is planned.

## 6 Data handling conventions

### 6.1 General conventions

#### 6.1.1 Missing data

##### Handling of missing/partial dates

In general, imputation of missing dates will be made for AE onset date, AE resolution date, date of death, medication start/end dates, start and end dates of prior and subsequent therapies, and date of initial diagnosis for reporting. No imputation should be done at the data level.

- If dates are completely missing, no imputation will be made.
- For any partial date with missing year, no imputation will be made.
- For missing initial diagnosis date and subsequent therapies, if only day is missing, then the 15th of the month will be used; if only year is present, then June 30th will be used. If such imputed date for initial diagnosis is on or after date of first dose, then date of first dose - 1 will be used. If such imputed date for subsequent therapies is before date of last dose, then date of last dose +1 will be used.
- If the imputed date is for an AE start date and is in the same year and month as but before the first dose date, then the first dose date will be used, or if the imputed AE start date is after the AE end date, then the AE end date will be used. If the imputed date is for an AE start date and is in the same year and month as but after the last dose date + 84 days, then the last dose date + 84 days will be used.
- If a medication date or time is missing or partially missing, so it cannot be determined whether it was taken prior or concomitantly, it will be considered as a prior and concomitant medication.
- If the imputed date is for a date of death and is before the last date that the patient is known to be alive, the latter date will be used.

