### 4.8.2 Adverse Events, Serious Adverse Events, and Deaths

#### 4.8.2.1 Analyses of adverse events

The primary focus of adverse event reporting will be on TEAEs. An adverse event (AE) will be considered to be a TEAE if it begins or worsens on or after first dose date and until 84 days (12 weeks) after the last dose date, or start of a new anticancer therapy/procedure, whichever comes earlier.

An AE occurring before the first dose or more than 84 days (12 weeks) after last dose date or after the start of a new anticancer therapy/procedure will not be included in TEAE displays, but will be listed as non-TEAEs.

If an AE date/time of onset (occurrence, worsening, or becoming serious) is incomplete, an imputation algorithm will be used to classify the AE as pre-treatment, TEAE, or post-treatment. The algorithm for imputing date/time of onset will be conservative and will classify an AE as a treatment-emergent unless there is definitive information to determine it is a non-TEAE (pre- or post-treatment).

Details on classification of AEs with missing or partial onset dates are provided in Section 6.

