### 4.9.1 Overall Response Rate

Overall response rate is defined as the proportion of patients who achieve either CR or PR as best overall response as assessed by investigators according to the Lugano Classification criteria before the start of subsequent anticancer therapy or procedure.

The order of overall response category is: CR, PR, SD, NE, PD (including disease recurrence/relapse). The overall response category will be derived based on response assessment performed on or before the start of subsequent anticancer therapy/procedure. Patients without documented subsequent anticancer therapy and/or with missing start date of anticancer therapy will be considered as not having received subsequent anticancer therapy. If a patient only has one valid disease assessment which is SD, and the assessment is within 35 days after the first dose, the overall response for this patient will be considered as NE.

The overall response rate and the corresponding 95% two-sided exact confidence interval at each dose level will be presented. Subgroup analysis may be provided for disease subtype, disease stage, double/triple hit (yes/no), bulky disease (yes/no), age group, sex, country, response to the first line and/or most recent line of prior systematic therapy (relapse: CR+PR vs. refractory: SD+PD vs. other: NE + missing), and other relevant variables.

Percent change from baseline in the sum of product of diameters (SPD) for target lesions will be presented for available data in the efficacy analysis set by dose level. These data will also be displayed as a waterfall plot, with vertical bars representing the sorted values of best percent reduction for each patient.

Tumor response and lesion measurement will be listed by assessment visit.

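### A partial start date of subsequent therapy can be imputed more than 6 days before documented progression, which censors a PFS or DOR event and can shorten the TEAE window

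*SAP*

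**What the plan says.** SAP 6.1.1 covers partial start dates of subsequent therapy with three rules:

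- Day missing: "if only day is missing, then the 15th of the month will be used".
- Day and month missing: "if only year is present, then June 30th will be used".
- Lower bound: "If such imputed date for subsequent therapies is before date of last dose, then date of last dose +1 will be used".

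For wholly missing dates the same section says "If dates are completely missing, no imputation will be made", and dates without a year are treated alike. SAP 4.9.1 adds, for response, that patients "with missing start date of anticancer therapy will be considered as not having received subsequent anticancer therapy".

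The start of subsequent therapy then acts as a cut-off. Under SAP 4.9.4, "Patients who have the event after the start of subsequent anticancer therapy/procedure" lose that event and "will be censored at the time of their last valid disease assessment on or before the start of subsequent anticancer therapy/procedure or clinical cut-off". SAP 4.9.2 applies the same rule to DOR. Both sections let PD count as an event if it lies within 6 days of the new therapy. SAP 4.8.2.1 ends the TEAE window at last dose + 84 days or at the start of new therapy, whichever is earlier.

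**The concern.** New therapy usually follows progression, and the protocol is built that way. Protocol 4.1.9 places the end-of-treatment visit before any new anticancer treatment, and Protocol 4.1.11 stops the follow-up scans once new treatment starts. A documented PD is therefore good evidence that therapy had not yet begun. The imputation does not use it: 6.1.1 bounds the therapy date by last dose alone.

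Elsewhere 6.1.1 does use what is known. An imputed death date is bounded by the last date known alive, an imputed diagnosis date by first dose, and an imputed AE start by first dose, AE end and last dose + 84 days. Therapy start lacks the matching bound.

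The consequences are a real PFS or DOR event reported as a censored time, dated back to an earlier scan, and AEs moved from the TEAE tables to the non-TEAE listing. Protocol 7.3 plans Part 2 cohorts of approximately 10 to 20, so one reclassified patient is 1/20 to 1/10, or 5% to 10%, of a cohort.

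**Working it through.** The plan gives no figure that depends on this rule, so there is nothing to reproduce. The check applies the stated rules to dates. All calendar dates below are assumptions, because the documents contain no patient dates and no rate of partial dates.

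**Rules applied**

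- Imputed start = the 15th, or 30 June; if that is before last dose, last dose + 1 (SAP 6.1.1).
- PD is an event if it is on or before therapy start, or within 6 days of it; otherwise it is censored (SAP 4.9.2, 4.9.4).
- TEAE window in days = the smaller of 84 and (therapy start − last dose) (SAP 4.8.2.1).

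**Worked cases** (the true status is an event in all four)

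| Case | Last dose | PD | True start | Imputed start | PD − imputed start | Status after imputation | TEAE days, true to imputed |
|---|---|---|---|---|---|---|---|
| Day missing | 1 Mar | 25 Mar | 29 Mar | 15 Mar | 10 days | censored | 28 to 14 |
| Day missing, bound applies | 16 Mar | 25 Mar | 29 Mar | 17 Mar | 8 days | censored | 13 to 1 |
| Year only | 20 May | 10 Sep | 1 Oct | 30 Jun | 72 days | censored | 84 to 41 |
| Year only, bound applies | 10 Jul | 21 Aug | 15 Sep | 11 Jul | 41 days | censored | 67 to 1 |

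**How often, if the day is missing.** Take PD and therapy in the same month, with the last-dose bound not moving the date. PD up to day 15 + 6 = 21 is protected, and PD from day 22 on is censored. Count the day pairs with PD on or before therapy:

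- 30-day month: 30 × 31 / 2 = 465 pairs. Pairs with PD on days 22 to 30: 9 + 8 + ... + 1 = 45. Share 45/465 = 9.7%.
- 31-day month: 31 × 32 / 2 = 496 pairs. Pairs with PD on days 22 to 31: 10 + 9 + ... + 1 = 55. Share 55/496 = 11.1%.
- If PD is instead uniform over the days of the month, the share is 9/30 = 30% (10/31 = 32% in a 31-day month).

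**How often, if only the year is known.** The assumed grid had last dose on each of the first 339 days of a year, PD 21, 42, 63 or 84 days later, and therapy 0, 7, 14, 28 or 56 days after PD within the same year. Of the true events, 3135/5825 = 54% became censored. The TEAE window was shortened in 60% of cases and lengthened in 26%. These shares describe the grid and are not estimates for this trial.

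**Errors in the other direction.** With the day missing, therapy may truly have started more than 6 days before a PD that falls on day 21 or earlier. Such a case should be censored but is counted as an event. For PD on days 8 to 21 there are 1 + 2 + ... + 14 = 105 such pairs. With the last-dose bound not in play, the TEAE window can be up to 31 − 15 = 16 days too short or 15 − 1 = 14 days too long.

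**The case against.** The strongest defence is that a mid-month rule with a last-dose bound is a defined convention, partial dates are probably few, PFS and DOR are secondary, and SAP section 4 rules out hypothesis testing. All of that stands and limits the weight of the point.

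A second defence is textual. SAP 6.1.1 says imputation is for reporting and must not alter the stored data, and SAP 4.7.3 only lists subsequent therapies, so imputed dates might never reach the PFS, DOR or TEAE derivations. This does not resolve the matter. No other rule for partial therapy dates is given, and the last-dose adjustment suggests that the imputed dates are meant to be used. At the least the SAP should say so.

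Four stronger readings are tempting, and the documents do not support them:

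- *The error always removes events and TEAEs.* It does not. The imputed date can also fall too late, as the 105 pairs and the 14-day lengthening show.
- *Wholly missing dates cause the same loss.* They are not imputed. If the response rule in 4.9.1 carries over, the event is kept and the TEAE window stays at 84 days. That errs the other way, and the rule is not repeated under PFS, DOR or TEAE.
- *The SAP contradicts its own conservative TEAE rule.* The sentence "The algorithm for imputing date/time of onset will be conservative" concerns incomplete AE onset dates, not therapy dates.
- *AEs vanish.* They leave the TEAE tables but are still listed as non-TEAEs.

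**Conclusion.** The point holds for partial dates. As written, SAP 6.1.1 can place the start of subsequent therapy more than 6 days before a documented PD. The efficacy rules then censor a true event, and the TEAE window can close early. With the day missing, this affects PD from day 22 of the therapy month: about 10-11% of PD-on-or-before-therapy day pairs, or about 30% under uniform PD dates. Both figures assume that PD and therapy fall in the same month and that the last-dose bound does not move the date. With only the year known, the displacement can be weeks to months.

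The error is not strictly one-directional. The overall effect depends on how many therapy dates are partial, which the documents do not give. This is a minor point, worth making because the correction is almost free.

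**What to change.** In SAP 6.1.1:

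1. For PFS and DOR, set a partial start of subsequent therapy to the latest of the current imputed date, last dose + 1, and the documented PD date when PD lies in the known month (or the known year, if only the year is present).
2. For the TEAE cut-off, use the latest date compatible with the partial date, still capped at last dose + 84 days.
3. State that these dates feed the PFS, DOR and TEAE derivations.

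In the four worked cases the efficacy start becomes 25 March, 25 March, 10 September and 21 August, so every PD is kept as an event. The TEAE windows become 30, 15, 84 and 84 days, against true values of 28, 13, 84 and 67.

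The cost is a few sentences and a small derivation change. The downside is that some patients whose therapy truly preceded PD, mainly those with year-only dates, will be counted as events, and some AEs after new therapy will be counted as TEAEs. Because Protocol 4.1.11 ends follow-up scans at new treatment, a PD documented well after therapy start should be uncommon.

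A cut-off at the end-of-treatment visit for wholly missing dates is not recommended. Protocol 4.1.11 continues scans after that visit until PD or new treatment, so such a cut-off would censor genuine PD found on those scans.

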##### Handling of missing relationship to investigational product of TEAEs

If the assessment of the relationship to investigational product is missing, then the relationship to investigational product has to be assumed and the TEAE considered as such in the frequency tables of possibly related TEAEs, but no imputation should be done at the data level.

##### Handling of missing severity/grades of AEs

If the severity/grade is missing for one of the treatment emergent occurrences of an AE, the maximal severity of the remaining occurrences will be considered. If the severity is missing for all the occurrences a “missing” category will be added in summary table.

No other imputation of values for missing data will be performed.

### **6.1.2 Unscheduled visits**

Unscheduled visit measurements of laboratory data, vital signs, and ECG will be used for computation of baseline and worst values and/or grades. Re-windowing for unscheduled visits will not be performed

### **6.1.3 Duplicated visits**

Depending on the statistical analysis method, single values may be required for each analysis window. For example, change from baseline by visit usually requires a single value per visit. Unless otherwise noted throughout the rest of this document, when a single value is needed, the following rule(s) will be used:

- If more than 1 assessment occurs during the same nominal visit, select the record closest to the nominal day for that visit.
- If there are 2 assessments that are equidistant from the nominal day, the data of the assessment after the scheduled study day will be used.
- The last measurement will be used if multiple measurements are taken on the same day.

**Appendix 1 Glossary of Abbreviations**

Glossary of Abbreviations:	
ADA	Anti-drug antibody
AE	Adverse event
AI	Accumulation index
AUC	Area under the concentration-time curve
B-NHL	B-cell lineage non-Hodgkin lymphoma
CBC	Complete blood count
CD	Cluster of differentiation
CI	Confidence interval
CL	Clearance
Cmax	Maximum concentration
CR	Complete response
CRF	Case report form
CSR	Clinical study report
CTCAE	Common Terminology Criteria for Adverse Events
DAR	Drug-to-antibody ratio
DESC	Dose Escalation Steering Committee
DLT	Dose-limiting toxicity
DOR	Duration of response
ECG	Electrocardiogram
ECOG	Eastern Cooperative Oncology Group
EOS	End of study
EOT	End of treatment
IP	Investigational product
MedDRA	Medical Dictionary for Regulatory Activities
MTD	Maximum tolerated dose
NCA	Noncompartmental
NE	Not evaluable
NHL	Non-Hodgkin lymphoma
ORR	Overall response rate

OS	Overall survival
PBD	Pyrralobenzodiazepine
PD	Pharmacodynamics, progressive disease
PFS	Progression-free survival
PK	Pharmacokinetic
PR	Partial response
PT	Preferred term
Q6W	Every 6 weeks
QTc	Corrected QT interval (ms)
SAE	Serious adverse event
SAP	Statistical analysis plan
SD	Stable disease
SMQ	Standardised MedDRA Query
SOC	System organ class
SPD	Sum of product of diameters
std	Standard deviation
TEAE	Treatment-emergent adverse event
TFLs	Tables, figures, and listings
TTR	Time to response
$\lambda_z$	Terminal elimination phase rate constant
$T_{max}$	Time to maximum concentration
$t_{1/2}$	Terminal half-life
$V_{ss}$	Volume of distribution at steady-state
$V_z$	Volume of distribution
WBC	White blood cells
WHO-DD	World Health Organization-Drug Dictionary
